B3b1. Design. A cluster-randomized clinical trial design will be used in which 36 group homes (14 male, 14 female, and 8 co-ed) will be randomly assigned to either the STEPS intervention (n = 18; 7 male, 7 female, and 4 co-ed homes) or attention-control (n = 18; 7 male, 7 female, and 4 co-ed homes). We have worked with or are currently working with eight agencies, five of which were in the original nine that were randomly ordered for participation. Two more of the original nine requested to be contacted again in early 2019, related to absence of key staff for one and merger with another agency for the other. Within some agencies, we will be able to identify six homes (2 of each gender and 2 co-ed) that meet criteria. Within agencies with only 3 homes for any or all three genders (male, female, co-ed) we will randomize homes within gender. If recruitment rates render a randomized home ineligible, we will randomly select an alternative home from a different agency. For agencies with only 1 eligible home for any gender, we will draw additional homes from a different agency. Whenever possible, we will adjust ordering of agencies to allow all participating homes within an agency to participate within the same time frame so that they are part of the same cohort. In addition, we may need to recruit additional agencies in order to reach the required number of 36 homes for this research. We will inform the IRB of any new agencies and provide letters of support. Group homes (residents and staff) will be recruited after randomization to simplify the process of explaining the study to individuals with ID. If fewer than two residential staff and/or fewer than three residents are willing to consent to participation, that group home will be ineligible and the third group home serving the same gender within that agency will be approached for recruitment.

Group homes in both conditions will receive one session (STEPS or attention-control Food for Life) every other week for 12 weeks, for six total sessions, and a booster at 18 weeks. Data collection for both conditions will be at baseline (pre-intervention) and 12 weeks (post-intervention), to estimate intervention effects and at 24 and 36 weeks after the start of the intervention to estimate maintenance.

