Setting and subjects. Agencies have on average 25 group homes, each serving 4-8 individuals with ID. The setting for the study will be group homes for individuals with mild to moderate ID located in the Chicago area. Individuals with mild to moderate ID have an IQ of 50-75 and basic reading and writing skills ranging from being able to write their names and addresses to writing simple sentences; hold jobs in work centers, supported employment of independent community employment; may take public transportation independently; and need support in instrumental activities of daily living such as budgeting, making appointments, and nutrition planning. The group homes accept only residents aged 18 or over. Each group home has two or more residential staff working an afternoon/evening shift when residents eat the evening meal and engage in afternoon/evening activities. Most group homes were formerly single-family homes (not specifically built to be group homes) and look like other homes in the neighborhoods. Homes typically have a living room, dining room, kitchen, bedrooms, and often a recreation room. Homes have laundry facilities, a common TV in the living room, and recreational materials. Residential staff and residents cook meals. Staff and residents do the regular cleaning, and agencies have

maintenance staff for heavier cleaning and repairs. Residents often have their own TVs in their bedrooms and usually share a bedroom with one roommate. Residential staff in Illinois are only required to have an 8th grade education, though most agencies require 12th grade.⁶³ They receive assistance from QIDPs who are required to have a Bachelor's degree in a human service field and at least one year of experience working with individuals with ID.⁵¹

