Intervention: Intervention sessions for STEPS and attention-control sessions will be held virtually. The interventionist and research assistant will conduct the session. They will ask the participants in the group to use a dining room or kitchen table as a place to talk and look at materials. Based on our pilot study (B3a), sessions will be held from approximately 6:30–7:45 p.m. on a weeknight. The evening before the session, the interventionist will reconfirm the time. All sessions are audiotaped for fidelity using the audio only record function in Webex.. Audiotapes from Sessions 1 and 6 will be used to score the IGES. Interventionists will bring audiotapes to the project office. Interventionists and research assistants will meet every other week with the PI and intervention coordinator.

12- and 24-week data collection:. The procedures will be the same as baseline. Participants (individuals with ID and residential staff) will be given a \$20 gift card after each data collection.

B3b8. Data analysis. All tracking of participants will follow CONSORT⁸⁵ and be entered into the RedCap database. SPSS for Windows (v. 23) and SAS (v. 9.3) will be used for data management and statistical analysis. Descriptive statistics for all variables will be obtained; *t* tests and chi-square analyses will be performed on demographics, baseline life events, environment, and current health (depression symptoms and medication management) to determine if intervention and control groups are comparable. Missing data will be imputed using SAS software and the multiple imputation strategy described by Rubin.⁸⁶ *To reduce Type-I error associated with multiple dependent variables, a .01* significance level will be used for all tests. From previous research, we expect all outcome measures to be close to normally distributed. We will use Tukey's⁸⁷ ladder of transformation to achieve normality, if needed. Outcome measures that cannot be successfully transformed to achieve normality will be analyzed separately using the rank-ordered multilevel analysis available in SAS.

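### The baseline comparability tests make no stated allowance for home clustering; run on residents, they would reject too often for variables correlated within homes and not balanced by the allocation.

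*Combined protocol and SAP*

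**What the plan says.** B3b1 (Design) sets the unit of randomisation: "A cluster-randomized clinical trial design will be used in which 36 group homes" are allocated 18 to each arm, split by home gender (control arm: "attention-control (n = 18; 7 male, 7 female, and 4 co-ed homes"). It also fixes the order of events: "Group homes (residents and staff) will be recruited after randomization to simplify the process of explaining the study to individuals with ID".

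B3b8 (Data analysis) says that t "tests and chi-square analyses will be performed on demographics, baseline life events, environment, and current health", the stated purpose being "to determine if intervention and control groups are comparable". For the level, a .01 "significance level will be used for all tests". No cluster adjustment is given, and nothing says whether a test has one row per resident or one per home.

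Clustering is recognised elsewhere. Under Specific Aim 1 the efficacy model has the group home as its top level, and under Specific Aim 2 the mediation models are multilevel.

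**The concern.** Ordinary t and chi-square tests assume independent observations. Residents of one home share staff, location and often sex, and B1 says that depressive symptoms are more common among females. Life events are staff-reported, so residents of a home may also share a reporter. Positive correlation within homes is therefore plausible for depression and life events. The environment variables describe the home itself.

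The comparison also has more to do here than in a trial that enrols before allocation. Residents and staff consent after their home's arm is known, and B3b9 concedes that randomising after recruitment and baseline would be ideal. A by-arm baseline comparison is a natural place to look for differential recruitment. If it over-rejects from clustering alone, ordinary chance differences between 18 and 18 homes may be reported as non-comparable arms and cannot be told from selection.

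**Working it through.** **Inputs from the documents**
- Homes: 36, 18 per arm (B3b1).
- Nominal level: .01 (B3b8). Sidedness is not stated; two-sided is assumed.
- Participants per home, m: homes are described as "each serving 4-8 individuals with ID" (Setting and subjects), and the inclusion criteria require at least 3 to agree. No average is given, so m = 3, 5 and 8 are used.

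**Assumed, because the documents give no value**
- ICC from .02 to .30 for resident-level variables.
- ICC = 1 for a variable that is constant within a home, if it is analysed by resident.

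The plan states no design effect or false-positive rate beyond the nominal .01, so there is no figure of its own to reproduce.

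**Formula.** A test that ignores clustering understates the variance of the arm difference by the design effect DE = 1 + (m − 1) × ICC. Its actual rejection rate under no true difference is 2 × [1 − Φ(2.576 / √DE)].

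- m = 5, ICC .02: DE = 1 + 4 × .02 = 1.08; 2.576/√1.08 = 2.479; rate 1.3%.
- m = 5, ICC .30: DE = 1 + 4 × .30 = 2.20; 2.576/√2.20 = 1.737; rate 8.2%.
- m = 5, ICC 1: DE = 5; 2.576/√5 = 1.152; rate 24.9%.

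Because nominal is 1%, each percentage below is also the multiple of nominal.

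| m | ICC .02 | ICC .05 | ICC .10 | ICC .30 | ICC 1 (home-level variable tested on residents) |
|---|---|---|---|---|---|
| 3 | 1.2% | 1.4% | 1.9% | 4.2% | 13.7% |
| 5 | 1.3% | 1.9% | 2.9% | 8.2% | 24.9% |
| 8 | 1.6% | 2.7% | 4.8% | 14.3% | 36.2% |

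The rate doubles at an ICC of about .11 for m = 3, .056 for m = 5 and .032 for m = 8.

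**Check by simulation** (18 v 18 homes, 10,000 trials per setting). At m = 5 and ICC .05 the t test rejects in 2.0% and the chi-square test in 1.9% (binary variable, assumed prevalence 33%). At ICC .30 the figures are 8.2% and 8.6%, and at ICC 1 they are 25.7% and 25.0%. A t test on the 36 home means rejects in 0.8% to 1.2% at every m and ICC tried, which is nominal within simulation error.

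**Effect of stratification.** The formula assumes unstratified allocation. With homes balanced 7/7/4 by gender in each arm, m = 5 and co-ed homes assumed half female, a chi-square test on resident sex rejected in none of 10,000 simulated trials. That test is conservative, so the inflation does not apply to every variable.

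**The case against.** **The unit is not stated.** A reader might infer that every test, including those on environment, will be run on residents. The documents do not say so. Table 3 lists environment as agency and home characteristics with no participant type, and Specific Aim 1 keeps home measures apart from individual ones. This stands: the last column of the table is conditional, and an environment test run once per home has no inflation.

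**Stratification protects some variables.** The section on recruitment, consent and retention assigns homes within agency and by home gender, so anything that tracks those factors is partly balanced. This stands too, but the protection is not assured. Replacement homes may come from other agencies, and B3b1's update before the pandemic pause counts 15 male homes already begun or finished against 14 planned.

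**Other checks exist.** A reader might infer that these tests are the plan's only look at recruitment. They are not. B3b8 also plans CONSORT tracking and descriptive statistics, and Specific Aim 1 builds propensity measures from background variables. The t and chi-square tests are, however, the only by-arm significance tests of comparability that are stated for these variables.

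**Little depends on them.** A reader might infer that a false imbalance would carry into the treatment estimate. No stated rule does this. Propensity measures are kept or dropped by their own significance in the outcome model. The one baseline check that feeds the propensity analysis is by agency and interventionist, on problem-solving skills and behaviours. This stands and limits the importance of the point.

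**An over-rejecting test at least errs towards flagging.** This is true, but a flag that clustering alone can raise is poor evidence of selection.

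**Conclusion.** The point holds in a limited form. As written, B3b8 specifies tests whose p-values would be too small if computed on residents, for variables correlated within homes and not balanced by the allocation. The likely size for resident-level variables is about 1.3 to 8 times the nominal .01 with 5 participants per home, and about 1.2 to 14 times over 3 to 8 per home, both for an assumed ICC of .02 to .30. These are illustrations, not documented facts, because neither the ICC nor the mean number of participants per home is given. The 14 to 36 times range requires a home-level variable to be tested on residents and left unbalanced by stratification.

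Over-rejection here means false alarms when arms differ only by chance. Because recruitment follows allocation, some observed differences could be real, and the test as specified would not tell the two apart. The consequence is confined to the conclusion about comparability.

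**What to change.** Amend B3b8 to:

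1. State the unit of analysis for each baseline variable.
2. Report balance by arm with standardised differences, at resident level and at home level.
3. Compare environment variables once per home (n = 36).
4. If a test is kept as a check on recruitment after allocation, use a mixed or GEE model with home as the cluster and a small-sample correction, or a permutation test over homes that respects the stratification.

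Standardised differences describe imbalance but do not by themselves separate selection from chance between 18 and 18 homes. They should be read alongside the CONSORT recruitment counts.

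The cost is a wording change and minor programming, with no new data. There is a small downside: a valid cluster-level test on 36 homes at .01 is less sensitive to real imbalance, so a non-significant result should not be taken as proof that recruitment was even.

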will modify the regression models discussed in MacKinnon (p. 49). MacKinnon's models generate three regression equations and then examine the impact of a single mediator in terms of reduced variance explained in the outcome from the direct predictor variable when the mediator variable is included in the model. The same approach will be used in this analysis, except that we will examine multilevel regression instead of simple With this modified approach, we will estimate three sets of regression equations for each regression models. of the three potential mediators making up the support environment for SPS, crossed with each of the measures of SPS skills and A/CBs of individuals with ID. Intervention condition will be included as predictor variables in these mediation models. The first set of regression equations estimates the simple effect of the intervention on the SPS skills and A/CBs of the individuals with ID (Aim 1). The second set estimates the effect of the intervention on the mediator variables (residential SPS, group SPS, or group cohesiveness). The third set estimates the combined effects of the intervention and mediators on the group measures of SPS skills and A/CBs of the individuals with ID. We will examine the impact of the change in the estimated coefficients associated with the introduction of each mediator. Significant mediators will be left out of subsequent models because of concerns about collinearity. Retention of a significant mediator may make it difficult to detect mediation effects in subsequent analyses. Though several mediation models are being estimated in this aim, the analysis is based on the assumption that significance values are of limited use in analysis to find mediation effects. Our analyses should allow us to evaluate whether the support environment for SPS mediates the relation between the intervention and the outcomes and should give us information on which mediation variables are responsible for the effect. Identifying key mediators will contribute to enhancing the intervention, improving long-term costeffectiveness, and designing future interventions. The same type of analysis will be conducted to determine the effects of the Food for Life nutrition intervention and the mediating effects of residential staff nutrition knowledge of the nutrition knowledge, weight and BMI of participants with ID.

Specific Aim 3. Evaluate the cost-effectiveness of STEPS relative to usual care.

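### Aim 2 uses single-mediator models, drops significant mediators and specifies no joint model, so it can credit a mediator that does nothing itself but is correlated with the one that does

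*Combined protocol and SAP*

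**What the plan says.** Section B3b8, Specific Aim 2, names three candidate mediators: residential staff social problem solving (SPS), group SPS and group cohesiveness. The method it adopts is one that will "examine the impact of a single mediator in terms of reduced variance explained in the outcome from the direct predictor variable" when the mediator is added. The text continues: "The same approach will be used in this analysis, except that we will examine multilevel regression instead of simple" regression. Sets of equations are to be fitted for each "of the three potential mediators making up the support environment for SPS, crossed with each of the measures of SPS skills and A/CBs".

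The rule at issue follows: "Significant mediators will be left out of subsequent models because of concerns about collinearity". The reason given is that "Retention of a significant mediator may make it difficult to detect mediation effects in subsequent analyses".

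The same paragraph says the analyses "should give us information on which mediation variables are responsible for the effect", and that identifying key mediators will help to improve the intervention and design later ones. It also holds that "significance values are of limited use in analysis to find mediation effects". No model containing all three mediators is described anywhere in the document.

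**The concern.** Asking which mediator is responsible means separating the three from one another. A model with one mediator cannot do that when the mediators move together within arm, because whichever one is in the model picks up part of the effect of those left out. The dropping rule reinforces this: once a mediator is significant, those examined after it are never adjusted for it. The rule also makes significance the trigger, in a paragraph that gives significance little weight.

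At stake is the explanatory conclusion. A later version of the intervention could be built around a component that changed alongside the active one but did nothing itself. The Aim 1 efficacy analysis is not touched.

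**Working it through.** The documents give no power or error figure for Aim 2, so there is none to reproduce.

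**Inputs from the document.** 36 homes, 18 per arm (B3b1). Significance level .01 for all tests (B3b8; sidedness not stated, two-sided assumed). Pilot effects of 0.60 for staff SPS, 0.51 for group SPS and 1.43 for cohesiveness (B3a, Results Phase 2). The pilot figures are pre-post changes, not between-arm differences.

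**Assumptions not in the document.** Within-arm correlation between mediators rho from 0 to .7, true b-path b from 0.3 to 0.8, and no direct effect of condition on the outcome.

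**Step 1: the bias.** Let mediator k be M_k = a_k X + e_k, with unit within-arm variance and corr(e_1, e_k) = rho. Let the outcome be Y = b M_1 + c'X + e, so that only M_1 acts. Regress Y on X and an inert M_k alone. The coefficient of M_k is the within-arm covariance of M_k and Y divided by the variance of M_k, which is rho × b. The apparent indirect effect is therefore a_k × rho × b. With all three mediators in the model it is 0. The sample size does not enter. With 2,000 simulated homes, pilot a-paths, b = 0.3 and rho = .5, the inert estimates stay at 0.08 and 0.22 (formula: 0.51 × .5 × 0.3 = 0.077; 1.43 × .5 × 0.3 = 0.215).

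**Step 2: how often an inert mediator is declared.** Home-level simulation: all three mediators shifted 1 SD, residual SD of the outcome √(1 − b²) (0.6, 0.87 and 0.95 for b = 0.8, 0.5 and 0.3), and both paths required at p < .01. Rates are per inert mediator and carry Monte Carlo error of a point or two.

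| b | rho .3 | rho .5 | rho .7 |
|---|---|---|---|
| 0.8 | 7% | 25% | 50% |
| 0.5 | 2% | 7% | 19% |
| 0.3 | 1% | 2% | 5% |

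The joint model gives about 1% or less in every cell.

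**Step 3: pilot effects as a-paths, staff SPS the true mediator.** Inert cohesiveness shows the larger mean indirect effect when 1.43 × rho × b > 0.60 × b, that is, when rho > 0.60/1.43 = 0.42. At b = 0.5 and rho = .5 the expected values are:
- staff SPS: 0.60 × 0.5 = 0.30
- group SPS: 0.51 × .5 × 0.5 = 0.13
- cohesiveness: 1.43 × .5 × 0.5 = 0.36

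A second simulation used 4 residents per home and an intraclass correlation of 0.1 (both assumed). The home-mean residual SD is then √(0.1 + 0.9/4) = 0.57, so a given b is a stronger signal than in Step 2. At b = 0.5 and rho = .5, cohesiveness was declared on both paths in 22.6% of runs and the true mediator in 18.4%. In the joint model the figures were 0.8% and 16.3%.

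**Step 4: the dropping rule itself.** In the Step 3 setting, mediators were examined in sequence with the true one first, and flagged on the b-path at b = 0.5. If significant mediators are dropped, the two inert ones are flagged in 26.2% and 17.4% of runs at rho .5, and in 61.7% and 51.5% at rho .7. If they are kept, the rates are 1.3% to 1.7%.

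**Step 5: what the joint model costs.** Power to declare the true mediator in the Step 2 setting, single against joint model:
- b = 0.5: 41% against 26% at rho .5; 42% against 16% at rho .7
- b = 0.3: 11% against 6% at rho .5; 12% against 4% at rho .7
- b = 0.8: 61% against 59% at rho .7. Here the b-path is near ceiling and the a-path test limits power, so the cost is hidden.

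**Step 6: where the problem disappears.** At rho = 0 there is no excess. If the intervention does not move the inert mediator (a_k = 0), its mean indirect effect is about 0 and it is declared on both paths in at most 0.7% of runs. If cohesiveness is the true mediator, it is wrongly outranked in under 2% of runs.

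**The case against.** The strongest defence is the plan's own: keeping a significant mediator makes later ones harder to detect. Step 5 shows that this is true, and the loss can be large. A reader might infer that a joint model costs nothing in power; that holds only when the b-path is assumed very strong. But the defence accepts bias in exchange for precision, on a question that is about separating the mediators.

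Second, the text is ambiguous. The third set of equations is described thus: "The third set estimates the combined effects of the intervention and mediators on the group measures of SPS skills and A/CBs". The plural could mean that several mediators enter together, and in a sequential reading a non-significant mediator might stay in. So the document does not support the inference that no model will ever adjust for the true mediator. Equally, if each mediator is always modelled alone, the dropping rule has nothing to drop and deleting it changes nothing. The root of the problem is the missing joint model; under a sequential reading the rule makes it worse. Neither reading supplies a model in which a significant mediator stays alongside those examined after it.

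Third, no within-arm correlation is reported, and the measures come partly from different sources: staff self-report, coded video and session audiotapes (Table 3). That limits how confidently a size can be given. Correlation remains plausible, since the plan itself anticipates collinearity and the staff and group video scales are scored from one group recording (B3b7).

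Fourth, the plan looks at changes in coefficients more than at significance, so declaration rates describe its behaviour only in part. The bias in Step 1, however, is in the coefficients themselves.

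**Conclusion.** The concern stands as a risk of misattribution. As written, Aim 2 can credit an inert mediator when two conditions hold together: it is correlated within arm with the true mediator, and the intervention moves it. The bias is a_k × rho × b and does not shrink with more homes.

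The direction is firm; the size is not. Across the assumed values, the false-declaration rate per inert mediator runs from about 1% (b = 0.3, rho .3) to about 50% (b = 0.8, rho .7), and no single figure in that range should be quoted as the trial's error rate. The threshold of rho above about 0.42 for cohesiveness to outrank staff SPS depends on using the pre-post pilot effects as a-paths.

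A reader might go further and conclude that Aim 2 will give the wrong answer. The documents do not support that: they report no correlations and no b-paths, and there are configurations in which the ranking comes out right.

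**What to change.** In B3b8, Specific Aim 2:

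- Delete the rule that leaves out significant mediators.
- Keep the single-mediator models and label them descriptive.
- Pre-specify one joint multilevel model per outcome, with condition and all three mediators, and say which of the two staff SPS measures enters it.
- Report each specific indirect effect with a Monte Carlo interval or a bootstrap interval that resamples homes.
- Base any statement about which mediator is responsible on the joint model alone.
- Report the within-arm correlations among the mediators, and state that correlated mediators may not be separable with 36 homes.

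The cost is revised wording and one extra model per outcome, with no new data and no change to conduct. The statistical cost is lower power to confirm a specific mediator (Step 5). In many plausible settings the joint model will single out none, and the plan should say so in advance.

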Methods. We will evaluate the cost-effectiveness of STEPS from the societal perspective, taking into account costs borne by the program, group home, health care system, public services, participant, and family. STEPS will be compared to usual care (control group costs of A/CBs excluding costs of the nutrition intervention). We will conduct additional analyses separately from the perspective of the program, group home, health care system, public services, and participant. For cost measurement, quantities of resources used and their associated prices will be collected for the program (either prices paid or value of staff time), group home (value of staff time) and participant (value of participant's time to participate in STEPS). For the effectiveness measurement, effectiveness will be measured using the number of A/CB incidents. We will also quantify the cost of each A/CB incident to calculate the net cost (or savings) of STEPS relative to standard of care. A/CB costs include for group home, participant and family members, public service (value of police officer time, ambulance), and health care system (cost per ED visit, urgent care or other physician visit, hospitalization) costs. To calculate total program-related costs, the program, group home, and participant costs will be summed to calculate total cost per participant. Similarly, total A/CB costs will be summed across the group home, participant and family, public service and health care system. All costs will be valued in 2016 dollars.

Data for the cost-effectiveness analysis will be drawn from study records, incident reports, and group home staff time logs (Table 4). Cost-effectiveness will be evaluated by combining the mean total program-related cost per participant with the number of A/CBs. We will calculate the incremental cost-effectiveness ratio (ICER)

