for STEPS relative to usual care, such that ICER = (C - C)/(E - E), where C is program cost and E is effectiveness. Subscript 1 denotes STEPS and subscript 0 denotes usual care. 95% confidence intervals for the ICERs will be calculated to evaluate the uncertainty of these results. We will conduct one-way and multiway sensitivity analyses for the key parameters to evaluate whether the ICERs are sensitive to plausible changes in their values. The sensitivity analysis is a check on the robustness and will determine the key parameters impacting the ICERs. We will also plot acceptability curves based on varying threshold (willingness to pay) values for a one-incident reduction in the number of A/CBs. Also, because A/CB incident costs will be collected, we will calculate the net cost (or net savings) associated with STEPS, such that the net cost = program-related cost – A/CB incident cost.

Specific Aim 4: Evaluate the effect of the Food for Life intervention and the mediating effect of the nutrition knowledge of residential staff on nutrition knowledge, weight and BMI of participants with ID. We hypothesize that participants in the attention control Food for Life nutrition intervention will show greater improvement in nutrition knowledge and improvement in weight and BMI for overweight and obese individuals compared to the STEPS intervention.

B3b9. Potential problems and alternative strategies: (1) We have no assessment-only control, which may attenuate our findings. However, we are assessing the mediation effects of the support environment for SPS in our analysis. (2) The attention-control group may also be affected by being in a group intervention. We therefore minimized group process in our attention-control group. (3) The assessment process may affect the SPS skills of residents and residential staff and the A/CBs of residents. To minimize this possibility, no feedback will be given on responses to questionnaires about problem-solving or the problem-solving discussion used to code the IFIRS, and no practice of problem-solving is provided in the assessment process.

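### The Aim 3 cost-effectiveness ratio uses program-related cost only, although the stated perspective is societal; incident costs reach only a separate net-cost line

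*Combined protocol and SAP*

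**What the plan says.** All of this is in section B3b8, Specific Aim 3.

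- **Perspective.** The evaluation is made "from the societal perspective, taking into account costs borne by the program, group home, health care system, public services, participant, and family".
- **Comparator.** STEPS is compared with "usual care (control group costs of A/CBs excluding costs of the nutrition intervention".
- **Two cost totals.** For program-related cost, "the program, group home, and participant costs will be summed to calculate total cost per participant". A second total, for A/CB incidents, adds up group home, participant and family, public-service and health-care costs.
- **Which total is used.** "Cost-effectiveness will be evaluated by combining the mean total program-related cost per participant with the number of A/CBs". The formula that follows agrees: "where C is program cost and E is effectiveness".
- **Uncertainty.** 95% confidence intervals and sensitivity analyses are specified for the ICERs. Acceptability curves are drawn over willingness to pay for one incident fewer. No other cost definition is given for any of these.
- **Incident costs.** They are used for a net cost or saving of STEPS, printed as program-related cost minus A/CB incident cost.
- **Other perspectives.** "We will conduct additional analyses separately from the perspective of the program, group home, health care system, public services, and participant".

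**The concern.** Health-care, public-service and family costs occur only in the incident total, and that total does not enter the ICER. The ratio and curves therefore answer a narrower question than the stated one: what the program costs per incident averted, not what society pays on balance. If incidents are costly and STEPS averts them, the ratio makes STEPS look more expensive to society than it is. The innovation section (B2) presents the cost analysis as a way to quantify what A/CBs cost individuals, their support systems and society, so the difference bears on the purpose of the aim.

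**Working it through.** The documents state no ICER, program cost, cost per incident or incident difference, so there is no figure to reproduce. The definition can be checked by algebra.

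**Notation (per participant).** P1, P0: program-related cost under STEPS and usual care. e1, e0: incidents. A1, A0: A/CB incident cost. dE = e0 − e1: incidents averted. The plan measures E as a count of incidents, so E1 − E0 is negative when STEPS works. I use incidents averted so that the sign is clear.

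**Step 1, ratio as written.** Nutrition-program cost is excluded and usual care has no STEPS cost, so P0 = 0.

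Stated ICER = (P1 − P0)/dE = P1/dE.

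The numerator is positive whatever happens to incident costs, so it cannot show a saving.

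**Step 2, ratio for the declared perspective.**

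Societal ICER = [(P1 + A1) − (P0 + A0)]/dE = stated ICER + (A1 − A0)/dE.

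This needs no assumed figures.

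**Step 3, equal mean incident cost c in both arms.** Then A1 − A0 = c·e1 − c·e0 = −c·dE, so

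Societal ICER = stated ICER − c.

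The societal ratio shows a saving when c exceeds P1/dE.

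**Step 4, illustration.** All values are assumed. With P1 = $600 and dE = 1, the stated ICER is $600 per incident averted.

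| Assumed c | Stated ICER | Societal ICER |
|---|---|---|
| $100 | $600 | 600 − 100 = $500 |
| $500 | $600 | 600 − 500 = $100 |
| $1,500 | $600 | 600 − 1,500 = −$900 (saving) |

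Over P1 = $300 to $1,200, dE = 0.5 to 2 and c = $100 to $1,500, the stated ICER runs from $150 to $2,400 and the societal ICER from −$1,350 to $2,300.

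**Step 5, acceptability curve.** At threshold λ the stated net benefit is λ·dE − P1. The societal one is (λ + c)·dE − P1, which is the same curve moved left by c. With P1 = $600, dE = 1, assumed standard errors of 0.6 incidents and $60, c treated as fixed, and λ = $500:

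- Stated: z = (500 − 600)/√((500 × 0.6)² + 60²) = −0.33, probability 0.37.
- Societal: probability 0.50, 0.75 and 0.88 for c = $100, $500 and $1,500.

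**Step 6, does the net-cost line repair this?** Take P1 = $600, c = $500, e0 = 4 and e1 = 3 (assumed).

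- Formula as printed, with STEPS-arm incident cost: 600 − 500 × 3 = −$900, an apparent saving.
- Formula with incident cost averted: 600 − 500 × (4 − 3) = $100, a net cost.
- With no effect at all (e1 = 4), the printed form gives 600 − 500 × 4 = −$1,400, and the averted form gives $600.

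Read literally, more incidents look like more savings. The text also describes the result as relative to standard of care, so a between-arm difference was probably meant, but the formula does not say so.

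**The case against.** **Incident costs may have been intended in C.** Describing usual care by the control group's A/CB costs would have no role in the ICER if C were program cost only. This stands as evidence of intent and is a reason to speak of an inconsistency. But two separate sentences place program-related cost alone in the ratio, and if incident costs belong in C0 they belong in C1 too. Either way the text must be reconciled.

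**Incident costs are analysed, through net cost.** True: they are not absent from Aim 3. That line, however, has no stated interval, and its formula has the fault shown in step 6.

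**Program cost per incident averted is a legitimate ratio.** A willingness to pay per incident averted may already include the money an incident costs, so subtracting that cost in the numerator could count it twice. The ratio together with a separate net cost would be a coherent scheme. It is not a societal ICER, which is what the plan calls for.

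**Stronger readings a reader might infer, which the documents do not support:**

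- *That the health-care and public-services ICERs are zero whatever the trial finds.* The plan promises additional analyses from those perspectives but does not say that they are ICERs or that they use program cost. A plain comparison of their costs fits the text equally well.
- *That any rise in incident cost under STEPS would be hidden.* More incidents at positive program cost would show in the ICER itself as STEPS being dominated, and the net-cost result is meant to show it too. The ICER would miss a cost increase only if incidents fell in number while their total cost rose.

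**Conclusion.** The concern holds in this form: the cost in the ICER does not match the declared societal perspective or the description of the comparator. The intervals and acceptability curves inherit the mismatch, and the net-cost line as printed does not make it good. The size is exact in algebra: the stated ICER differs from the societal one by the between-arm difference in incident cost per incident averted. This equals c if mean incident cost is the same in both arms. In dollars the size is unknown, since every dollar figure above is an assumption; the figures show that a conclusion could change, not that it will. P0 = 0 rests on the stated exclusion of nutrition-program cost. The point is limited to Aim 3 and does not touch efficacy, randomization, data collection or safety. It should be corrected before the economic analysis is run.

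**What to change.** In Specific Aim 3:

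1. For the societal ICER, define C1 and C0 as program-related cost plus A/CB incident cost per participant in each arm, with nutrition-program cost still excluded.
2. Express E as incidents averted. Base the confidence intervals, sensitivity analyses and acceptability curves on this C. State that the threshold values an averted incident apart from costs already counted in C.
3. Write net cost as program-related cost minus the between-arm reduction in A/CB cost, and give it an interval.
4. Keep the present ratio as a secondary result labelled *program cost per incident averted*.
5. For the health care system and public services, which bear no listed program cost, report the between-arm cost difference.

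This is a change of wording. The cost table before the timeline (section B3b10) already lists repair or replacement, family time, police time, emergency visits, hospital stays and physician visits. Ambulance cost is named in the Methods text but does not appear in the table as extracted; the table is broken, so this only needs checking. The price is a more variable numerator and wider intervals.
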